#### **5.5.1 Acceptable Concomitant Medications**

All treatments that the investigator considers necessary for a subject's welfare may be administered at the discretion of the investigator in keeping with the community standards of medical care. All concomitant medication will be recorded on the case report form (CRF) including all prescription, over-the-counter (OTC), herbal supplements, and IV medications and fluids. If changes occur during the trial period, documentation of drug dosage, frequency, route, and date may also be included on the CRF.

All concomitant medications received within 28 days before the first dose of trial treatment and 30 days after the last dose of trial treatment should be recorded. Concomitant medications administered after 30 days after the last dose of trial treatment should be recorded for SAEs and ECIs as defined in Section 7.2.

#### **5.5.2 Prohibited Concomitant Medications**

Subjects are prohibited from receiving the following therapies during the Screening and Treatment Phase (including retreatment for post-complete response relapse) of this trial:

- Antineoplastic systemic chemotherapy or biological therapy
- Immunotherapy not specified in this protocol
- Chemotherapy not specified in this protocol

- Investigational agents other than MK-3475
- Radiation therapy
  - Note: Radiation therapy to a symptomatic solitary lesion or to the brain may be allowed after consultation with Sponsor.
- Live vaccines within 30 days prior to the first dose of trial treatment and while participating in the trial. Examples of live vaccines include, but are not limited to, the following: measles, mumps, rubella, chicken pox, yellow fever, , rabies, BCG, and typhoid (oral) vaccine. Seasonal influenza vaccines for injection are generally inactivated flu vaccines and are allowed; however intranasal influenza vaccines (e.g., Flu-Mist®) are live attenuated vaccines, and are not allowed.
- Glucocorticoids for any purpose other than to modulate acute symptoms from an adverse event. The use of physiologic doses for subjects requiring ongoing corticosteroids, may be approved after consultation with the Sponsor.

Subjects who, in the assessment by the investigator, require the use of any of the aforementioned treatments for clinical management should be removed from the trial. Subjects may receive other medications that the investigator deems to be medically necessary.

The Exclusion Criteria describes other medications which are prohibited in this trial.

There are no prohibited therapies during the Post-Treatment Follow-up Phase.

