### **5.5 Concomitant Medications/Vaccinations (allowed & prohibited)**

Medications or vaccinations specifically prohibited in the exclusion criteria are not allowed during the ongoing trial. Listed below are some specific restrictions for concomitant therapy or vaccination during the course of the trial. If there is a clinical indication for one of these or other medications or vaccinations specifically prohibited during the trial, discontinuation from trial therapy or vaccination may be required. The investigator should discuss any questions regarding this with the local Clinical Monitor. The final decision on any supportive therapy or vaccination rests with the investigator and/or the subject's primary physician. However, the decision to continue the subject on trial therapy or vaccination schedule requires the mutual agreement of the investigator, the Sponsor and the subject.

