### **5.7.3 Use in Pregnancy**

If a subject inadvertently becomes pregnant while on treatment with MK-3475, the subject will immediately be removed from the study. The site will contact the subject at least monthly and document the subject's status until the pregnancy has been completed or terminated. The outcome of the pregnancy will be reported to the Sponsor without delay and within 24 hours if the outcome is a serious adverse experience (e.g., death, abortion, congenital anomaly, or other disabling or life-threatening complication to the mother or newborn). The study investigator will make every effort to obtain permission to follow the outcome of the pregnancy and report the condition of the fetus or newborn to the Sponsor. If a male subject impregnates his female partner the study personnel at the site must be informed immediately and the pregnancy reported to the Sponsor and followed as described above and in Section 7.2.2.

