## **5.8 Subject Withdrawal/Discontinuation Criteria**

Subjects may withdraw consent at any time for any reason or be dropped from the trial at the discretion of the investigator should any untoward effect occur. In addition, a subject may be withdrawn by the investigator or the Sponsor if enrollment into the trial is inappropriate, the trial plan is violated, or for administrative and/or other safety reasons. Specific details regarding discontinuation or withdrawal procedures; including specific details regarding withdrawal from Future Biomedical Research, are provided in Section 7.1.4 – Other Procedures.

A subject must be discontinued from the trial for any of the following reasons:

- The subject or legal representative (such as a parent or legal guardian) withdraws consent.

A subject must be discontinued from treatment (but may continue to be monitored in the post-treatment follow-up portion of the trial) for any of the following reasons:

- The subject or legal representative (such as a parent or legal guardian) withdraws consent for treatment
- Confirmed radiographic disease progression

*Note:* For unconfirmed radiographic disease progression, please see Section 5.2.2.

*Note:* A subject may be granted an exception to continue on treatment with confirmed radiographic progression if clinically stable or clinically improved, please see Section 7.1.2.5.1.

- Unacceptable adverse experiences as described in Section 5.2.1.2
- Intercurrent illness that prevents further administration of treatment
- Investigator's decision to withdraw the subject
- The subject has a confirmed positive serum pregnancy test
- Noncompliance with trial treatment or procedure requirements
- The subject is lost to follow-up
- Completed 24 months of treatment with MK-3475

*Note:* 24 months of study medication is calculated from the date of first dose. Subjects who stop MK-3475 after 24 months may be eligible for up to one year of additional study treatment if they progress after stopping study treatment provided they meet the requirements detailed in Section 7.1.5.2.1.

- Administrative reasons

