#### **7.1.1.6.3 Subsequent Anti-neoplastic Therapy Status**

The investigator or qualified designee will review all new anti-neoplastic therapy initiated after the last dose of trial treatment. If a subject initiates a new anti-neoplastic therapy within 30 days after the last dose of trial treatment, the 30 day Safety Follow-up visit must occur before the first dose of the new therapy. Once new anti-neoplastic therapy has been initiated the subject will move into survival follow-up.

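### Sections 5.5.2 and 5.7.3 take a subject out of the trial where other sections only end treatment and continue follow-up; read literally, they cut off survival follow-up and could bias overall survival upward

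*Combined protocol and SAP*

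**What the plan says.** **Leaving the trial.** Section 5.5.2 lists therapies prohibited in the Screening and Treatment Phase and says that subjects who "require the use of any of the aforementioned treatments for clinical management should be removed from the trial". Section 5.7.3 says that if a subject becomes pregnant on treatment, "the subject will immediately be removed from the study".

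**Leaving treatment but staying in follow-up.**
- Sections 1.0 and 2.1 follow all subjects by telephone for overall survival. The only end points are death, withdrawal of consent and the end of the study.
- Section 5.8 has two lists. The list for mandatory exit from the trial has one entry, withdrawal of consent. The other opens "A subject must be discontinued from treatment (but may continue to be monitored in the post-treatment follow-up portion of the trial" and includes a confirmed positive pregnancy test, intercurrent illness and the investigator's decision.
- Section 7.1.1.6.3 states: "Once new anti-neoplastic therapy has been initiated the subject will move into survival follow-up". Section 7.1.5.4.1 says the same and sets telephone contact about every 12 weeks.
- Section 5.5.2 itself adds: "There are no prohibited therapies during the Post-Treatment Follow-up Phase".

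**Neither.** Section 5.5 says that if a prohibited medication is indicated, "discontinuation from trial therapy or vaccination may be required", and that "the decision to continue the subject on trial therapy or vaccination schedule requires the mutual agreement of the investigator, the Sponsor and the subject". It does not address follow-up.

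**The concern.** Chemotherapy and radiation head the reasons for which a subject on treatment might fall under 5.5.2, and the need for either often signals clinical deterioration. If the subject leaves the trial at that moment, survival is censored at the last assessment (Table 11), probably shortly before a poor outcome. Kaplan-Meier estimation assumes that censored subjects have the same outlook as those who remain; here they would not.

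Overall survival is a secondary objective. Section 7.1.5.5 was written so that survival data are current and complete at database locks, and a removal rule works against that. Because both readings can be defended from the text, sites may also act differently, and the follow-up of similar subjects would then depend on the site.

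**Working it through.** The plan gives no figure on this point, so the check is first a comparison of text, then an illustration.

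**1. The same event under different sections**

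| Event on treatment | Section | Consequence stated |
|---|---|---|
| Needs a listed therapy | 5.5.2 | Leaves the trial |
| Same | 5.5 | Trial therapy may have to stop; nothing on follow-up |
| Starts new anti-neoplastic therapy | 7.1.1.6.3, 7.1.5.4.1 | Survival follow-up |
| Pregnancy | 5.7.3 | Leaves the study, yet monthly contact until the pregnancy ends |
| Same | 5.8 | Treatment ends; may still be monitored |
| Any subject | 1.0, 2.1 | Survival follow-up to death, withdrawal of consent or study end |

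A subject who needs chemotherapy falls under the first and third rows at once, and the two outcomes are incompatible.

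**2. Which data the literal reading would cost**
- *Survival:* all contact after removal, which 1.0, 2.1 and 7.1.5.4.1 would otherwise collect.
- *Progression:* little for anti-cancer therapies. Section 7.1.2.5.3 and the flow-chart notes already stop imaging at new anti-cancer treatment. The added loss is mainly for items such as steroids or live vaccines.
- *AEs and SAEs:* Sections 7.2, 7.2.3.1 and 7.2.3.2 count reporting windows from cessation of treatment, not from leaving the trial: 30 days for AEs; 90 days for SAEs and events of clinical interest, or 30 if new anticancer therapy starts. Section 7.1.4.1 requires final-visit activities and follow-up of ongoing AEs at discontinuation or withdrawal. Whether 5.5.2 overrides these is unclear.

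**3. Illustration for overall survival**

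Every input here is an assumption; none is in the documents. A fraction f is removed. Subjects never removed have exponential survival with median 10 months (hazard a = ln2/10). Time to removal is exponential with median 4 months (b = ln2/4), no death occurs before removal, and survival is censored at removal. There is no other censoring.

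The observed hazard is a(1−f)/[(1−f) + f·e^(−dt)] with d = b − a = 0.104. Setting its integral equal to ln2 gives the Kaplan-Meier median:

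T = (1/d) · ln[(2^(d/a) − f)/(1−f)], with d/a = 1.5 and 2^1.5 = 2.828.

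For f = 0.10: (2.828 − 0.10)/0.90 = 3.032; ln 3.032 = 1.109; 1.109/0.104 = 10.67 months.

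The true median solves (1−f)·2^(−t/10) + f·S(t) = 0.5, where S is survival from baseline in removed subjects:
- Residual median 4 months after removal: S(t) = 2^(−t/4)·(1 + t·ln2/4).
- Residual median 10 months: S(t) = (5/3)·2^(−t/10) − (2/3)·2^(−t/4).

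| Removed | KM median | True, residual 4 | Overstated | True, residual 10 | Overstated |
|---|---|---|---|---|---|
| 1% | 10.06 | 9.99 | 0.7% | 10.06 | 0.0% |
| 5% | 10.32 | 9.98 | 3.5% | 10.31 | 0.1% |
| 10% | 10.67 | 9.95 | 7.2% | 10.63 | 0.4% |
| 20% | 11.44 | 9.91 | 15.4% | 11.27 | 1.5% |
| 30% | 12.35 | 9.87 | 25.1% | 11.92 | 3.7% |

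The Kaplan-Meier median does not depend on what happens after removal. The bias is therefore set by how many are removed and how poor their outlook is.

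**The case against.** The best reply is that, taken as a whole, the protocol already protects follow-up. Section 5.5.2 covers only the Screening and Treatment Phase. A deteriorating subject would normally stop MK-3475 first, under 5.8 (progression, intercurrent illness, investigator's decision) or Table 4 (clinically unstable). Chemotherapy would then start in the follow-up phase, where nothing is prohibited. Section 7.1.5.5 lets the Sponsor request survival status for all subjects without a recorded death. Section 5.5.2 says should, not must, and 5.8 also permits discretionary withdrawal, for example when the trial plan is violated. Overall survival is secondary and summarized without a hypothesis test.

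This stands as a limit on how often the conflict would bite, and it is why the small-fraction rows of the table may be the realistic ones. It does not remove the conflict. The sentence in 5.5.2 applies when the need arises during treatment, and a site that has taken a subject out of the trial could reasonably think that later survival requests no longer cover that subject.

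Several stronger readings are tempting but unsupported:
- *Section 5.5 keeps subjects in follow-up.* It is silent on this. Section 5.8 says only that monitoring may continue, and it does not list need for a prohibited therapy.
- *Section 5.5.2 contradicts its own list or Table 3.* The radiation provision ("Radiation therapy to a symptomatic solitary lesion or to the brain may be allowed after consultation with Sponsor") and the steroid provisions are ordinary exceptions. Table 3 concerns steroids for immune-related events, and 5.5.2 exempts steroids used for acute AE symptoms.
- *The literal rule ends AE and SAE collection.* The windows run from cessation of treatment, so this is a conflict between passages, not a certain loss.

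**Conclusion.** The contradiction is real and concerns a stated rule, not a missing detail. Sections 5.5.2 and 5.7.3 cannot both be followed alongside 1.0, 2.1, 5.8, 7.1.1.6.3 and 7.1.5.4.1. For pregnancy the practical effect is smaller, because 5.7.3 keeps monthly contact until the pregnancy ends.

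The main consequence is possible informative censoring of overall survival, with a Kaplan-Meier estimate that is likely too high, and follow-up that may vary by site. The direction assumes that removed subjects have a worse outlook than those who stay. The size is unknown. The range of below 1% to about 25% is an illustration that also assumes every removed subject is lost to survival follow-up; it should not be quoted as an expected bias.

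A reader might also infer a large loss of progression data or bias in the primary response rate. The documents do not support the first for subjects who start anti-cancer therapy, since their imaging stops anyway. On the second, a subject removed before any post-baseline scan, for a reason other than progression or a drug-related AE, would fall outside the FAS (Section 8.2.4.1). The flow charts call for imaging at treatment discontinuation, which limits this, and nothing in the documents allows it to be sized.

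**What to change.** Reconcile 5.5.2 and 5.7.3 with 1.0, 2.1, 5.8, 7.1.1.6.3 and 7.1.5. In both places, replace removal from the trial or study with a statement to this effect: whatever is decided about treatment, the subject stays in the trial for the safety, disease-status (where still applicable) and survival follow-up already specified, unless consent is withdrawn.

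The treatment decision for each listed therapy, and for pregnancy, is a clinical matter and is not addressed here.

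The cost is two sentences in the next amendment and a note to sites. No new visits or procedures are needed, because the follow-up is already described. If any subject has already been taken out under the literal wording, the number and the dates of last survival contact should be reported with the overall survival results.

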## **5.6 Rescue Medications & Supportive Care**

### **5.6.1 Supportive Care Guidelines**

Subjects should receive appropriate supportive care measures as deemed necessary by the treating investigator. Suggested supportive care measures for the management of adverse events with potential immunologic etiology are outlined below. Where appropriate, these guidelines include the use of oral or intravenous treatment with corticosteroids as well as additional anti-inflammatory agents if symptoms do not improve with administration of corticosteroids. Note that several courses of steroid tapering may be necessary as symptoms may worsen when the steroid dose is decreased. For each disorder, attempts should be made to rule out other causes such as metastatic disease or bacterial or viral infection, which might require additional supportive care. The treatment guidelines are intended to be applied when the investigator determines the events to be related to pembrolizumab.

Note: if after the evaluation the event is determined not to be related, the investigator is instructed to follow the ECI reporting guidance. Refer to Section 5.2.1 for dose modification.

It may be necessary to perform conditional procedures such as bronchoscopy, endoscopy, or skin photography as part of evaluation of the event.

- **Pneumonitis:**

- For **Grade 2 events**, treat with systemic corticosteroids. When symptoms improve to Grade 1 or less, steroid taper should be started and continued over no less than 4 weeks.
- For **Grade 3-4 events**, immediately treat with intravenous steroids. Administer additional anti-inflammatory measures, as needed.
- Add prophylactic antibiotics for opportunistic infections in the case of prolonged steroid administration.

- **Diarrhea/Colitis:**

Subjects should be carefully monitored for signs and symptoms of enterocolitis (such as diarrhea, abdominal pain, blood or mucus in stool, with or without fever) and of bowel perforation (such as peritoneal signs and ileus).

- All subjects who experience diarrhea/colitis should be advised to drink liberal quantities of clear fluids. If sufficient oral fluid intake is not feasible, fluid and electrolytes should be substituted via IV infusion. For Grade 2 or higher diarrhea, consider GI consultation and endoscopy to confirm or rule out colitis.
  - For **Grade 2 diarrhea/colitis** that persists greater than 3 days, administer oral corticosteroids.
  - For **Grade 3 or 4 diarrhea/colitis** that persists > 1 week, treat with intravenous steroids followed by high dose oral steroids.
  - When symptoms improve to Grade 1 or less, steroid taper should be started and continued over no less than 4 weeks.
- **Type 1 diabetes mellitus (if new onset, including diabetic ketoacidosis [DKA]) or  $\geq$  Grade 3 Hyperglycemia, if associated with ketosis (ketonuria) or metabolic acidosis (DKA)**
    - For **T1DM** or **Grade 3-4 Hyperglycemia**
      - Insulin replacement therapy is recommended for Type I diabetes mellitus and for Grade 3-4 hyperglycemia associated with metabolic acidosis or ketonuria.
      - Evaluate patients with serum glucose and a metabolic panel, urine ketones, glycosylated hemoglobin, and C-peptide.

- **Hypophysitis:**

- For **Grade 2** events, treat with corticosteroids. When symptoms improve to Grade 1 or less, steroid taper should be started and continued over no less than 4 weeks. Replacement of appropriate hormones may be required as the steroid dose is tapered.
- For **Grade 3-4** events, treat with an initial dose of IV corticosteroids followed by oral corticosteroids. When symptoms improve to Grade 1 or less, steroid taper should be started and continued over no less than 4 weeks. Replacement of appropriate hormones may be required as the steroid dose is tapered.

- **Hyperthyroidism or Hypothyroidism:**

Thyroid disorders can occur at any time during treatment. Monitor patients for changes in thyroid function (at the start of treatment, periodically during treatment, and as indicated based on clinical evaluation) and for clinical signs and symptoms of thyroid disorders.

- **Grade 2** hyperthyroidism events (and **Grade 2-4** hypothyroidism):
  - In hyperthyroidism, non-selective beta-blockers (e.g. propranolol) are suggested as initial therapy.
  - In hypothyroidism, thyroid hormone replacement therapy, with levothyroxine or liothyronine, is indicated per standard of care.
- **Grade 3-4** hyperthyroidism
  - Treat with an initial dose of IV corticosteroid followed by oral corticosteroids. When symptoms improve to Grade 1 or less, steroid taper should be started and continued over no less than 4 weeks. Replacement of appropriate hormones may be required as the steroid dose is tapered.

- **Hepatic:**

- For **Grade 2** events, monitor liver function tests more frequently until returned to baseline values (consider weekly).
  - Treat with IV or oral corticosteroids
- For **Grade 3-4** events, treat with intravenous corticosteroids for 24 to 48 hours.
- When symptoms improve to Grade 1 or less, a steroid taper should be started and continued over no less than 4 weeks.

- **Renal Failure or Nephritis:**
  - For **Grade 2** events, treat with corticosteroids.
  - For **Grade 3-4** events, treat with systemic corticosteroids.
  - When symptoms improve to Grade 1 or less, steroid taper should be started and continued over no less than 4 weeks.
- **Management of Infusion Reactions:** Signs and symptoms usually develop during or shortly after drug infusion and generally resolve completely within 24 hours of completion of infusion.

Table 5 below shows treatment guidelines for subjects who experience an infusion reaction associated with administration of pembrolizumab (MK-3475).

Table 5 Infusion Reaction Treatment Guidelines

NCI CTCAE Grade	Treatment	Premedication at subsequent dosing
Grade 1 Mild reaction; infusion interruption not indicated; intervention not indicated	Increase monitoring of vital signs as medically indicated until the subject is deemed medically stable in the opinion of the investigator.	None
Grade 2 Requires infusion interruption but responds promptly to symptomatic treatment (e.g., antihistamines, NSAIDS, narcotics, IV fluids); prophylactic medications indicated for <=24 hrs	
Stop Infusion and monitor symptoms.
 
Additional appropriate medical therapy may include but is not limited to:
 
 
IV fluids
 
Antihistamines
 
NSAIDS
 
Acetaminophen
 
Narcotics
 
 
Increase monitoring of vital signs as medically indicated until the subject is deemed medically stable in the opinion of the investigator.
 
If symptoms resolve within one hour of stopping drug infusion, the infusion may be restarted at 50% of the original infusion rate (e.g., from 100 mL/hr to 50 mL/hr). Otherwise dosing will be held until symptoms resolve and the subject should be premedicated for the next scheduled dose.
 
Subjects who develop Grade 2 toxicity despite adequate premedication should be permanently discontinued from further trial treatment administration.
	
Subject may be premedicated 1.5h (± 30 minutes) prior to infusion of pembrolizumab (MK-3475) with:
 
Diphenhydramine 50 mg po (or equivalent dose of antihistamine).
 
Acetaminophen 500-1000 mg po (or equivalent dose of antipyretic).

NCI CTCAE Grade	Treatment	Premedication at subsequent dosing

Grades 3 or 4
 
Grade 3: Prolonged (i.e., not rapidly responsive to symptomatic medication and/or brief interruption of infusion); recurrence of symptoms following initial improvement; hospitalization indicated for other clinical sequelae (e.g., renal impairment, pulmonary infiltrates)
 
Grade 4: Life-threatening; pressor or ventilatory support indicated
	
Stop Infusion.
 
Additional appropriate medical therapy may include but is not limited to:
 
 
IV fluids
 
Antihistamines
 
NSAIDS
 
Acetaminophen
 
Narcotics
 
Oxygen
 
Pressors
 
Corticosteroids
 
Epinephrine
 
 
Increase monitoring of vital signs as medically indicated until the subject is deemed medically stable in the opinion of the investigator.
 
Hospitalization may be indicated.
 
Subject is permanently discontinued from further trial treatment administration.
	
No subsequent dosing

Appropriate resuscitation equipment should be available in the room and a physician readily available during the period of drug administration.
		

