### **5.2.1.2 Dose Modification**

Adverse events (both non-serious and serious) associated with pembrolizumab exposure may represent an immunologic etiology. These adverse events may occur shortly after the first dose or several months after the last dose of treatment. Pembrolizumab must be withheld for drug-related toxicities and severe or life-threatening AEs as per [Table 3](#) below. See Section 5.6 and the Events of Clinical Interest Guidance Document for supportive care guidelines, including use of corticosteroids.

Table 3 Dose Modification and Toxicity Management Guidelines for Immune-related AEs Associated with Pembrolizumab

General instructions:				

 
1. Corticosteroid taper should be initiated upon AE improving to Grade 1 or less and continue to taper over at least 4 weeks.
 
2. For situations where pembrolizumab has been withheld, pembrolizumab can be resumed after AE has been reduced to Grade 1 or 0 and corticosteroid has been tapered. Pembrolizumab should be permanently discontinued if AE does not resolve within 12 weeks of last dose or corticosteroids cannot be reduced to <math>\leq 10</math> mg prednisone or equivalent per day within 12 weeks.
 
3. For severe and life-threatening irAEs, IV corticosteroid should be initiated first followed by oral steroid. Other immunosuppressive treatment should be initiated if irAEs cannot be controlled by corticosteroids.
 
				
Immune-related AEs	Toxicity grade or conditions (CTCAEv4.0)	Action taken to pembrolizumab	irAE management with corticosteroid and/or other therapies	Monitor and follow-up
Pneumonitis	Grade 2	Withhold	
 
• Administer corticosteroids (initial dose of 1-2 mg/kg prednisone or equivalent) followed by taper
 
	
 
• Monitor subjects for signs and symptoms of pneumonitis
 
• Evaluate subjects with suspected pneumonitis with radiographic imaging and initiate corticosteroid treatment
 
• Add prophylactic antibiotics for opportunistic infections
 

	Grade 3 or 4, or recurrent Grade 2	Permanently discontinue		

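### Section 5.6.1 ties IV steroids for Grade 3-4 diarrhea/colitis to more than a week of persistence, a longer wait than for Grade 2 and one that Table 3 does not contain; the condition should be deleted

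*Combined protocol and SAP*

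**What the plan says.** Section 5.6.1 introduces its content as follows: "Suggested supportive care measures for the management of adverse events with potential immunologic etiology are outlined below". It also says when the content applies: "The treatment guidelines are intended to be applied when the investigator determines the events to be related to pembrolizumab".

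For diarrhea/colitis the section asks for monitoring for enterocolitis and bowel perforation, fluids, and consideration of GI consultation and endoscopy from Grade 2 upwards. It then gives two lines on starting steroids:

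- Grade 2: an event "that persists greater than 3 days, administer oral corticosteroids".
- Grade 3 or 4: an event "that persists > 1 week, treat with intravenous steroids followed by high dose oral steroids".

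Section 5.2.1.2 also carries steroid guidance, in Table 3. The diarrhea/colitis row gives corticosteroids at 1-2 mg/kg prednisone or equivalent, then a taper, with no condition on persistence. General instruction 3 above the table reads: "For severe and life-threatening irAEs, IV corticosteroid should be initiated first followed by oral steroid".

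The two sections refer to each other. Section 5.2.1.2 names Section 5.6, together with the Events of Clinical Interest guidance document, as the place to look "for supportive care guidelines, including use of corticosteroids". After Table 3 it sends the reader to 5.6.1 again for adverse event management. The pointer back from 5.6.1 is narrower: "Refer to Section 5.2.1 for dose modification".

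**The concern.** The order by severity is reversed. The milder event is given steroids after more than 3 days. The event that Table 8 grades as severe with hospitalization indicated, or as life threatening and needing urgent intervention, is given them after more than a week.

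The wait cannot be read as time allowed for diagnosis, because the guidance applies once the investigator has attributed the event to pembrolizumab.

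What is at stake is subject safety. A site using 5.6.1 as its steroid guide could hold IV steroids for over a week in drug-related Grade 3-4 colitis, while the same section warns of bowel perforation. Safety and tolerability are primary objectives of the trial, but this point concerns the care of subjects and not the estimation of any endpoint.

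**Working it through.** The plan states no figure to reproduce. The check sets the instructions side by side.

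**Steroid timing for diarrhea/colitis**

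| Source | Grade | Steroid step | Stated wait |
|---|---|---|---|
| 5.6.1 | 2 | Oral | More than 3 days |
| 5.6.1 | 3-4 | IV, then high-dose oral | More than 1 week |
| Table 3, colitis row | 2 or 3 | 1-2 mg/kg prednisone or equivalent, then taper | None |
| Table 3, instruction 3 | Severe and life-threatening irAEs | IV, then oral | None |

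In days, 1 week = 7 days, and 7 − 3 = 4 days longer for Grade 3-4 than for Grade 2 (7/3 ≈ 2.3 times the Grade 2 wait).

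**Grade 3-4 steroid lines across 5.6.1**

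| Event | Timing stated for starting steroids |
|---|---|
| Pneumonitis | "immediately treat with intravenous steroids" |
| Hypophysitis | None |
| Hyperthyroidism | None |
| Hepatic | None (24 to 48 hours is a duration, not a delay) |
| Renal failure or nephritis | None |
| Diarrhea/colitis | After more than 1 week |

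That is 1 immediate, 4 with no timing and 1 with a wait: 1 + 4 + 1 = 6. Type 1 diabetes and hypothyroidism are not counted because their lines give no steroids. Infusion reactions are not counted because Table 5 lists corticosteroids only as one possible therapy.

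**Could another line in 5.6.1 supply an earlier step?** No. The Grade 2 line is labelled for Grade 2 only. The general measures for diarrhea/colitis are monitoring, fluids and consideration of GI consultation and endoscopy. The taper line applies once symptoms have improved.

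**Would a site meet the wait?** Yes, if it follows the cross-references. Section 5.2.1.2 directs it to 5.6 for steroid use and to 5.6.1 for adverse event management, and 5.6.1 points back to 5.2.1 only for dose modification.

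**Limits of the comparison.** Table 3 states no start time, and instruction 3 orders the routes of administration without setting a time from onset. The contrast is therefore between a stated wait and no stated wait, not between two stated times. In the text available, the Table 3 steroid cell for Grade 4 colitis is blank and may be a merged cell. For Grade 4 the contrast therefore rests on instruction 3 and Table 8.

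**The case against.** The strongest reply is that the protocol already handles severe colitis in Table 3. The Summary of Changes says that the dose modification guidelines were expanded in this amendment to cover supportive care, monitoring and follow-up, so as to be current and comprehensive. An investigator managing Grade 2-4 colitis has to consult the Table 3 row for the withhold or discontinue decision, and the steroid instruction sits in that row without a wait. The pointer from 5.6.1 to 5.2.1 leads there too, whatever its stated purpose. The 5.6.1 text is also permissive: care is at the investigator's judgment, and Section 5.5.2 allows glucocorticoids for acute symptoms of an adverse event. Nothing prevents treatment on day 1. Table 8 is a generic grading scale whose Grade 4 wording does not name steroids, and no document shows how often harm would follow.

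Much of this stands. The protocol as a whole does not forbid or uniformly delay steroids, and the defect is best described as a 5.6.1 line that was not harmonised with Table 3. These points limit the risk but give no reason to keep the wait. Where two parts of a protocol differ and neither is said to govern, discretion does not make the later-treatment wording right, least of all for the more severe grade. The expansion of Table 3 supports reading the 5.6.1 line as text left behind.

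A second reply is that deleting the phrase leaves the Grade 2 threshold of more than 3 days at odds with Table 3, which covers Grades 2 and 3 in one row. That is true, but the Grade 2 threshold is a matter of clinical judgment and does not weaken the case for the Grade 3-4 deletion.

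**Conclusion.** The concern holds. Section 5.6.1 states a wait of more than 7 days before IV steroids for Grade 3-4 diarrhea/colitis, against no stated wait in Table 3 and more than 3 days for Grade 2 in the same section. It is the only one of six Grade 3-4 steroid lines in 5.6.1 with a wait.

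The practical risk assumes that a site follows 5.6.1 literally for steroid use. Investigator discretion, monitoring for perforation, fluids, consideration of GI consultation and endoscopy, and the Table 3 withhold or discontinue rules all reduce that risk without removing the stated wait. The documents give no incidence of severe colitis, so the number of subjects affected is not estimated. The correction should be made on safety and consistency grounds. It changes no endpoint, analysis or sample size.

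**What to change.** In the Grade 3 or 4 diarrhea/colitis line of Section 5.6.1, delete the condition that the event has persisted for more than 1 week. The line then runs straight from the grade to IV steroids followed by high-dose oral steroids. This removes the reversed order by grade and agrees with Table 3 and its general instruction 3.

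Leave the Grade 2 threshold of more than 3 days to the sponsor's clinical judgment. If it is intended, state it in both 5.6.1 and the Table 3 colitis row.

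The cost is one phrase removed from one line, by amendment or clarification letter. Data collection, dose-modification rules, analysis and sample size are unchanged.
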